Patient Selection and Recruitment: Patients', who undergo AS of the abdominal and pelvic regions, within the scope of general surgical (GS), gastrointestinal (GI) and gynecological (GYN) specialties, shall be considered. Patients shall be considered for the study if they fulfill the following selection criteria. They would be screened on the day of their preoperative appointment, assessed for eligibility and then if they agree, obtain consent.

The inclusion criteria will include: age 18 yrs to 70 yrs-; ambulatory surgeries producing at least moderate pain-such as cholecystectomy, appendectomy, ovarian cystectomy, inguinal hernia repair, abdominal wall hernias; and an ability to communicate in English.

Exclusion criteria will include: allergy to M or HM; patient on regular chronic opioid medication; patient uncontrolled systemic disease; severe obesity with a BMI >35; significant psychological impairment; history of drug addiction or dependence; any planned regional or nerve block other than local anesthesia infiltration; patients with confirmed sleep apnea; emergency surgeries and urological surgeries.

Suitable patients will be screened before their visit to 'pre-anesthetic visit'. During their visit, they will be approached by a trained RA, involved with the study. Relevant information will be provided, along with a letter of information about the research study. Consent of willing patients will be obtained, along with their baseline, and demographic variables. The consent will include the study process, and also willingness to be followed, and contacted at 24 hours and at 3 months after surgery.

On the day of surgery, at DSU, patients' consent will be confirmed. Relevant baseline variables of the recruited patients shall be noted (appendix 1). The concerned OR anesthesiologist is informed of the patient's inclusion to the study and reinforced about the study methodology (appendix 2).

Most Effective Opioid Analgesia in Ambulatory Surgeries: a randomized control, investigator blinded, parallel group with superiority design study of Morphine versus Hydromorphone

[name], Principal Investigator SJHH

[name], Principal Investigator HHS

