Allocation and Randomization: Treatment allocation will be done using a random, computer generated table, with an allocation ratio of 1:1, using random permuted block sizes. Stratification based on each centre (3 sites). These syringes (4*10 mls)-in sealed packages, labelled with serial numbers and no identifiers for the medication, shall be deposited in a safe drug locker, within the fridge, at the respective PACU. The actual randomization, for each patient happens as they enter into the PACU after surgery. The PACU nurse allotted for that patient will obtain the next medication package in series to be used for that patient. To ensure that the respective patient and medication is matched for subsequent analysis, the nurse will attach the medication sequence number on the patient study records, with no identifiers of actual drug. The PACU nurse shall also note down the patient hospital ID on the medication syringe, once it is taken out, to ensure there is no mix up.

Blinding: The study allocation will be blinded to patients, treating nurses, physicians, research assistant and investigators. The allocation order will be available only to the person responsible for randomizing and the pharmacists involved in the study at each centre.

Application of Intervention:

The Operating Room Protocol: Patients included in the study need to be managed according the OR protocol provided in Appendix 2. In brief, the patient will only have a GA, with local infiltration provided at the end of the surgery. Long acting opioid medications (morphine and hydromorphone) are not administered in the OR. LA infiltration is done within a range of 20-30 mls (based on laparoscopic or open surgeries) using 0.25% bupivacaine with or without adrenaline.

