At the end of 2 hours or after satisfactory completion of primary endpoints, patients shall be transferred to DSU. At the DSU, in both groups, patients shall be given oral Oxycocet (combination of oxycodone and paracetamol) or Tylenol 3 (combination of codeine and paracetamol), as a PRN medication, if necessitated by the patient's pain. Nurses shall note down the occurrence of any pain and nausea necessitating treatment in the patient's CRF. Readiness to discharge home is noted down for each patient. The RA shall collect the CRFs from PACU and DSU and deposit safely in a locked filing cabinet.

Planned Outcomes: Our combined primary outcome will be proportion of patients with SAME, as compared between the 2 groups. Analgesia will be based on NAS 0-10 (appendix 3), and PONV will be based on VDS 0-5 (appendix 3). These observations will be made at the end of 2 hrs or before (corresponding to the time of discharge from PACU), by the PACU nurse, in the specified CRF. All the other outcomes to be recorded within the hospital, along with the time of their measurement and proposed analysis method are noted in table 1.

Sample Size Calculation: It was calculated based on the primary, binary outcome of proportion of patients with SAME, which will be compared using a chi-square test. According to literature,

Most Effective Opioid Analgesia in Ambulatory Surgeries: a randomized control, investigator blinded, parallel group with superiority design study of Morphine versus Hydromorphone
 [name], Principal Investigator SJHH
 [name], Principal Investigator HHS

approximately 30%-40% of patients are provided with inadequate analgesia after their AS,^(25, 26) with a similar number also known to suffer from PONV after AS.^(3, 24) Our chart reviews suggests that approximately 20% of patients suffer from inadequate analgesia with PONV using morphine. For a 2-sided test, with an alpha of 0.05 and a power of 90%, and with an estimated effect size of 10% (p1= 80% and p2= 90%), a sample size of 266 per group was calculated. However, for recruitment we shall have a target of 275 per group, for a total of 550 patients (rounding off). For the primary outcome analysis, we expect minimal loss through attrition as the study involves a follow up of few hours. The expected recruitment is approximately 20 cases per month at each of the 3 sites. We expect the trial to run for 10-12 months.

Table 1: Study Outcomes, and their Measurement and Analysis

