4	Global Impression of Change	Likert scale 1-7

Most Effective Opioid Analgesia in Ambulatory Surgeries: a randomized control, investigator blinded, parallel group with superiority design study of Morphine versus Hydromorphone
[name], Principal Investigator SJHH
[name], Principal Investigator HHS

5	Analgesic Use: Did you have to use any pain medications for more than 1 month, to help with pain, which started with or after Surgery?	Yes or No
---	---	-----------

Statistical Analysis: The study will be analyzed using an intention to treat approach. The individual outcomes along with their respective analyses method have been listed within the table 1. Broadly the dichotomous outcomes will be reported as proportions and analyzed using a chi-square test to detect a significant difference ($p<0.05$). Precision will be reported using 95% CI. Continuous outcomes will be analyzed using an unpaired 2-tailed student t test for significance ($p<0.05$). Means and standard deviations shall be reported along with 95% CI. We also plan to perform logistic multivariable regression analysis to account for the influence of baseline covariates, which are listed in appendix 1. A sensitivity analysis will be performed to compare the effects of laparoscopic surgeries vs open surgeries.

Trial Management: This trial will be conducted at 3 hospital sites affiliated with McMaster University, Hamilton: St Joseph's Hospital, McMaster University Hospital and Juravinski Hospital.

Data Management and Quality Control: All study data including CRFs of each patient, shall be securely stored at the central office. A summary table indicating study timeline from enrollment to final follow-up (<http://www.spirit-statement.org/title/>) shall be included for each patient.⁽²⁷⁾ CRF's will be collected as paper forms. They shall be periodically cross-checked for completeness and entered into a suitable electronic master file. All reports of incorrect randomizations, protocol violations or incomplete data shall be noted.

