APPENDIX 2: STANDARD ANESTHESIA PROTOCOL

- Only General Anesthetic
- No regional other than local infiltration as appropriate-to be documented
- Midazolam 1-2 mg –to be given as appropriate-to be documented
- Propofol-Induction in titrated doses
- Rocuronium-Muscle relaxant in titrated doses
- Intraop opioids: Remifentanil-bolus or infusion
 - Fentanyl-25-50 mcg bolus
 - Sufentanil-5-20 mcg bolus
- No long acting opioids to be given during the surgery
- No NSAIDS to be given during the surgery
- Antiemetic prophylaxis with Dexamethasone 4mg to 8mg soon after induction in all patients, except with history of allergy.

Protocol Version Date: Version 5 / June 23, 2015

Page 19 of 21

Most Effective Opioid Analgesia in Ambulatory Surgeries: a randomized control, investigator blinded, parallel group with superiority design study of Morphine versus Hydromorphone
[name], Principal Investigator SJHH
[name], Principal Investigator HHS

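### Allocation happens after surgery, but no check of the operating-room course precedes drawing the study package, so patients with a block, long-acting opioid or NSAID can dilute the primary comparison

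*Combined protocol and SAP*

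**What the plan says.** The document is a combined protocol and SAP.

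- **Eligibility.** Under Patient Selection and Recruitment, criteria are assessed at the preoperative appointment. The relevant exclusion is "any planned regional or nerve block other than local anesthesia infiltration", so a block that was not planned is not covered.
- **Day of surgery.** The same section states: "On the day of surgery, at DSU, patients' consent will be confirmed". Baseline variables are also noted, and the OR anesthesiologist is told that the patient is in the study and reminded of the Appendix 2 method.
- **OR conduct.** Appendix 2 has "No long acting opioids to be given during the surgery" and "No NSAIDS to be given during the surgery". The operating-room paragraph of the main text repeats the opioid restriction. Neither ban appears among the eligibility criteria.
- **Allocation.** Under Allocation and Randomization, "The actual randomization, for each patient happens as they enter into the PACU after surgery". The PACU nurse then takes the next package. No condition for withholding it is given.
- **Deviations and analysis.** Under Data Management and Quality Control, "All reports of incorrect randomizations, protocol violations or incomplete data shall be noted". The Statistical Analysis section specifies intention to treat, does not define the set further, and names no per-protocol analysis.
- **Recording.** The Appendix 1 anesthesia page lists dexamethasone, midazolam, propofol, three short-acting opioids, infusions, ondansetron and PACU delay. It has no item for a regional block, for OR morphine or hydromorphone, or for an OR NSAID.

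**The concern.** Randomising after surgery has one clear advantage: a patient whose anesthetic has already departed from the plan can be left out before allocation, with no bias and no breach of intention to treat. The plan takes on late randomisation without using that advantage. Once the package is drawn, removing the patient is no longer clean.

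Such departures are foreseeable. The Risk Assessment section concedes that relying on short-acting opioids alone may differ from some clinicians' usual practice. A patient who arrives in PACU with a working block, a long-acting opioid or an NSAID on board has pain partly governed by something other than the study drug. In such patients SAME is likely to differ less between arms. At stake is some of the power of the primary comparison.

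**Working it through.** **Inputs from Sample Size Calculation.** Alpha is 0.05, two-sided, and the power sought is 90%. The assumed rates and the result are stated as "with an estimated effect size of 10% (p1= 80% and p2= 90%), a sample size of 266 per group was calculated". The recruitment target is 275 per group, 550 in total. The test is chi-square.

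**Step 1: reproduce the plan's figure.** With mean proportion p̄ = 0.85, let s0 = √(2·p̄·(1−p̄)) = √(2·0.85·0.15) = 0.5050 and s1 = √(p1(1−p1) + p2(1−p2)) = √(0.16 + 0.09) = 0.5000.

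n = [(1.960·0.5050 + 1.282·0.5000)/0.10]² = 265.9, so 266 per group. This matches the plan.

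**Step 2: power at the recruitment target.** Power = Φ[(Δ·√n − 1.960·s0)/s1]. With n = 275 and Δ = 0.10: (1.6583 − 0.9897)/0.5000 = 1.337, so power is 0.909.

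**Step 3: add affected patients.** The documents give no rate, so the fraction v is an assumption. Affected patients are given a mean SAME rate of 85% and either none of the drug effect (85% in both arms) or half of it (82.5% against 87.5%). The mean proportion stays at 0.85, so s0 is unchanged and s1 barely moves. The difference becomes 0.10·(1 − v) with no effect, or 0.10·(1 − v/2) with half.

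| v (assumed) | Δ, no effect | Power | Δ, half effect | Power |
|---|---|---|---|---|
| 0% | 0.1000 | 0.909 | 0.1000 | 0.909 |
| 5% | 0.0950 | 0.879 | 0.0975 | 0.895 |
| 10% | 0.0900 | 0.842 | 0.0950 | 0.879 |

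For example, at v = 10% with no effect: (0.0900·16.583 − 0.9897)/0.5009 = 1.004, so power is 0.842.

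**Step 4: sensitivity to the 85%.** With no drug effect and a common SAME rate anywhere from 80% to 95% in affected patients, power is 0.896-0.901 at v = 2%, 0.875-0.888 at 5% and 0.832-0.862 at 10%. The margin between 266 and 275 therefore absorbs about 2% of such patients before power reaches about 90%.

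**Step 5: cost of not randomising them.** If they are left out before allocation and recruitment continues to 550 randomised, power stays at 0.909. Consented patients needed are 550/(1 − v): 550/0.95 = 578.9, so 579 at 5%, and 550/0.90 = 611.1, so 612 at 10%.

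**The case against.** **The gap is inferred from silence.** No text orders that a patient with an OR breach be randomised. The plan expects every patient to be managed per protocol in the OR, and it foresees reports of incorrect randomisations. This stands as a limit on the wording: a careful site might withhold a package. Without a written rule, though, sites could act differently.

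**The protocol has a control already.** A reader might infer that nothing but consent is confirmed on the day. That is not so: the anesthesiologist is briefed on Appendix 2. The briefing makes deviations less likely but does not say what happens when one occurs.

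**Re-checking eligibility would not help.** This is correct for OR opioids and NSAIDs, which are conduct rules. The remedy must be new conditions at the point of randomisation.

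**Affected patients could be found later.** Partly right. The anesthetic record exists, Appendix 2 asks for regional or infiltration use to be documented, and Appendix 1 records the actual procedure and whether it was laparoscopic or open. The form gap concerns drugs and blocks only.

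**The trial calls itself pragmatic.** Keeping minor deviations is defensible there, and the loss is small at low rates. But the events at issue come before allocation, so leaving these patients out costs nothing in validity.

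**Stronger readings that the documents do not support.**
- Bias between arms: the events precede a concealed, blinded allocation, so they should balance.
- Unchecked study-opioid titration after an OR opioid: the PACU Protocol makes the first dose conditional on the pain score and has withholding rules for sedation and respiratory depression.
- A large loss of precision for time to hospital discharge through inpatient conversions: the documents give no standard deviation, conversion rate or excess stay, and admissions decided after PACU entry would be randomised in any case.

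**Conclusion.** The point holds as a missing check before allocation, not as a flaw in the intention-to-treat principle. As written, nothing stops a patient with a known block, long-acting opioid or NSAID in the OR from being randomised and analysed. The expected harm is dilution: power of about 0.88-0.90 if 5% are affected and 0.84-0.88 if 10% are, against 0.909 with none. These figures rest on assumed rates, on an 85% mean SAME rate in affected patients, and on their keeping between none and half of the drug effect. At 2% or below the loss is negligible. The change is worth making because it is cheap and carries no risk of bias, not because the loss is known to be large.

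**What to change.** 1. **Allocation and Randomization:** add a documented check before any package is drawn. It should also apply when the OR anesthesiologist starts the protocol during a PACU hold (Appendix 1, anesthesia page, item 10). Do not randomise if the anesthetic record shows a regional or nerve block, morphine or hydromorphone, or an NSAID given in the OR, or if the operation is already known to have become non-ambulatory or an excluded type.
2. **Patient Selection and Recruitment:** extend the block exclusion from planned to planned or performed, keeping the exception for local infiltration.
3. **Appendix 1, anesthesia page:** add three yes/no items: block, morphine or hydromorphone in the OR, NSAID in the OR.
4. **Reporting:** log patients consented but not randomised, with reasons, and continue to 550 randomised.
5. **Statistical Analysis:** define the intention-to-treat set as everyone whose package was drawn, including patients admitted later.

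The cost is one amendment, a short checklist and slightly longer recruitment. At an assumed 5%, 579 − 550 = 29 extra consented patients are needed, about half a month at the plan's 3 × 20 = 60 cases a month.

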5–10 times more potent and enhances its distribution to cerebral tissues, making for easier titration.⁽⁹⁾ The t_{1/2} Ke0 (transfer life from plasma to effect site) is 1.6hr – 4 hr for M, compared to 18-38 min for HM.^(9,10) It is observed that health care providers may be willing to provide higher dose of HM compared to M in EMU, as its actual quantity of drug is much smaller and therefore appears to cause less concern.^(12, 13) Our literature review showed that there are no previous studies comparing these 2 medications in AS patients. The lone systematic review compared various acute and chronic pain studies, in various routes of drug administration.⁽⁹⁾ Of the 11 studies identified; only 4 were done in acute pain settings.⁽¹³⁻¹⁶⁾ Two of them were done by the same author in ER settings. Chang et al noted that HM reduced the mean pain scores by 1.3 units [95% CI= (-2.2 to -0.5)] compared to M in 198 adults treated in ER.^(12,13). However it did not show much difference in geriatric population.¹⁴ In perioperative settings, Hong et al studied the difference in nausea between the 2 medications in 50 patients using PCA and found no difference.⁽¹⁵⁾ Rapp et al studied various effects between the 2 medications in 61 surgical patients using PCA. There is not much clarity about their primary outcome; however they found the effects to be similar.⁽¹⁶⁾ Both these studies had smaller sample sizes. The meta-analysis performed demonstrated that the HM does provide better analgesia than M, with a small effect size; Cohen's d=0.266 (p=0.012).⁽⁹⁾ Looked at acute pain alone it was statistically significant (p=0.006), compared to chronic pain (p=0.889). It was noted that that there is a definite lack of comparative studies between them in surgical settings.

Patients Symptoms after Discharge

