Hence, we will also look for any differences in pain, nausea and vomiting over the first 24 hrs after the surgery, along with chances of readmission or ER visits within the same period, post discharge. At 3 months, we will look for the incidence of persisting pain after surgery.

Hypothesis

In patients who undergo ambulatory surgical procedures causing at least moderate pain, hydromorphone (HM) increases the proportion of patients who would demonstrate 'satisfactory analgesia [$=<4/10$ NAS] with minimal or no postoperative nausea-vomiting (PONV) [$<2/5$ VDS] as compared to morphine (M), when both are administered intravenously, in equianalgesic doses, and are compared at 2 hours after surgery in PACU.

2. Specific Objectives

The primary objective of this study is to compare the proportion of patients with SAME (satisfactory analgesia and minimal emesis) after AS, when using M compared with HM, during the immediate postoperative hospital stay.

Secondary objectives include:

1. Total dose of analgesic used in PACU, in morphine equivalents,
2. Time to discharge or readiness to discharge from the DSU,
3. Proportion of pain, and its comparison after discharge, within 24 hours,
4. Proportion of nausea, and its comparison after discharge, within 24 hours,
5. Proportion of vomiting, and its comparison after discharge, within 24 hours,
6. Incidence of CPSP at 3 months after discharge

The tertiary objectives include:

1. Proportion of patients with severe itching,

Protocol Version Date: Version 5 / June 23, 2015

Most Effective Opioid Analgesia in Ambulatory Surgeries: a randomized control, investigator blinded, parallel group with superiority design study of Morphine versus Hydromorphone

[name], Principal Investigator SJHH

[name], Principal Investigator HHS

2. Proportion of patients with significant sedation,
3. Proportion of patients with significant respiratory depression,
4. Patient satisfaction score at the time of discharge,
5. Time to discharge or readiness to discharge from the PACU,
6. Use of ketorolac as a rescue medication,

METHODS

The study is designed as a multisite, 2 arm, parallel, superiority design with randomization of patients and blinding of patients, health care providers (physicians and nurses) and research personnel (research coordinator and data analyst). Patients will be stratified based on site and laparoscopic/open surgeries. Intention to treat approach will be used for design and analysis.

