PACU Stay: The actual study intervention (hence randomization) will only become applicable once the patient is moved to the PACU. Every patient will be treated as per the protocol during the intraoperative management, which primarily restricts the use of any study opioids. The details are provided in appendix 2. The nurse looking after the study patient in PACU will administer the medication as per the study protocol. This would include analgesia with equipotent doses of M or HM administered in titrated doses. Syringes will be pre-prepared from the pharmacy in EMUs; 1ml=1mg of morphine or 0.2 mg of hydromorphone. We shall consider a potency ratio of 1:5 (M: HM), considered equivalent in literature.⁽⁹⁾ Analgesia will be provided according to the following guideline. A similar method has been advised to be safe and effective for titrated analgesia in PACU.⁽²⁴⁾ Readiness to discharge from PACU and outcomes are noted at 2 hrs, or at the time of discharge to DSU.

Most Effective Opioid Analgesia in Ambulatory Surgeries: a randomized control, investigator blinded, parallel group with superiority design study of Morphine versus Hydromorphone
[name], Principal Investigator SJHH
[name], Principal Investigator HHS

PACU Protocol (titrate the opioid medication to achieve desired pain score)

- Patient to be asked for their pain score, and if it is more than 4 out of 10 (NAS): to receive the 1st dose within 5 minutes after coming to PACU: 0.04mg/kg morphine units (rounding off to the nearest 1 ml or 0.5 ml); with a maximum of 3 mg of morphine equivalents.
- Repeat doses: 0.02 mg/kg morphine units every 5-10 minutes to titrate for analgesia and side effects (rounding off to the nearest 1 ml or 0.5 ml)
- If no side effects observed-titrate to have analgesia: NAS =<4/10.
- If Nausea-Vomiting observed: record it in the CRF provided and treat it with antiemetics (Ondansetron 1-4 mg IV, Dimenhydrinate 25-50 mg)
- If patient is too sedated (<3-Ramsey Sedation Scale)-withhold the next dose and restart the bolus if the score is >3
- If respiratory depression present, withhold the next dose, treat with Naloxone if necessary.
- Ketorolac IV 15-30 mg as rescue medication if patient does not tolerate the study opioid or if the patient does not satisfy the success of satisfactory analgesia at more than 1 hr.

DSU Stay and Protocol:

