OUTCOME MEASURE	TYPE	MEASUREMENT	TIME OF MEASUREMENT	ANALYSIS METHOD
Primary outcome Satisfactory Analgesia with minimal PONV	Binary	NAS=<4/10 VDS<2/5	At 2hrs or at the time of discharge from PACU	Chi-square
Severe Itching	Binary	VAS>5/10	At 2hrs or at the time of discharge from PACU	Chi-square or Fisher's test (as appropriate)
Severe Sedation	Binary	Ramsey Score >3/6	At 2hrs or at the time of discharge from PACU	Chi-Square or Fisher's test (as appropriate)
Severe Respiratory Depression	Count	All cases needing treatment as counts	At 2hrs or at the time of discharge from PACU	Chi-square or Fisher's test (as appropriate)
Use of Ketorolac	Continuous	Total dose used per patients as a rescue therapy	At 2hrs or at the time of discharge from PACU	T test
Mean dose of Analgesic Used	Continuous	Dose of Analgesic used per patient in EMU	At the time of hospital discharge	T test

Most Effective Opioid Analgesia in Ambulatory Surgeries: a randomized control, investigator blinded, parallel group with superiority design study of Morphine versus Hydromorphone
 [name], Principal Investigator SJHH
 [name], Principal Investigator HHS

Patient Satisfaction-Mean score (0-10)	Continuous	Mean Score calculated between 0 to 5 scale	At the time of hospital discharge	T test
Time to discharge from PACU	Continuous	Mean time in hrs	At 2hrs or at the time of discharge from PACU	T test
Time to discharge from the hospital	Continuous	Mean time in hrs	At the time of hospital discharge	T test

Outcomes at Post-operative Day 1:

Patients will be approached by 1-2 phone calls shall be done during the next day; if unanswered, a repeat call will be made on the subsequent day (2nd day after discharge); for responders, the following questions will be asked.

1. What was your average pain score over the last 24 hrs, in 0-10 NAS scale, after you were discharged home?
2. After discharge, did you have nausea-severe enough to require medications at home?
3. After discharge, did you have vomiting-severe enough to require medications at home?
4. After discharged home, did you require a visit to ER, or readmission?

Outcomes at 3 months:

Patients will be contacted by a mailed package at 3 months after surgery to collect the following outcomes.

1	Do you have Persistent Pain (which started with or after surgery), at or near the surgical area?	Yes or No
2	Intensity of Pain	NAS: 0-10
3	Brief Pain Inventory-Interference Items 7 Items: each item scored between 0-10	

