Risk Assessment and Protocol Adherence: This trial does not entail any higher risk than the standard of care to the patients. This is a pragmatic trial and involves the use of medications of known benefit and in clinically acceptable doses. It also involves using only short acting opioids in the form of fentanyl or sufentanil or remifentanil in small boluses or infusion. Although for some this might differ from their normal practice, we do not anticipate this to be a major issue as the surgeries would be of 1-2 hrs duration and can be effectively and safely managed with short acting opioids until patients are shifted to PACU. Protocol also involves the use of study medications in PACU at an initial dose of 0.05mg/kg, followed by 0.03/mg/kg EMU boluses. Studies have shown that IV Morphine titration in PACU, after moderately painful surgeries

Most Effective Opioid Analgesia in Ambulatory Surgeries: a randomized control, investigator blinded, parallel group with superiority design study of Morphine versus Hydromorphone

[name], Principal Investigator SJHH

[name], Principal Investigator HHS

require a mean morphine dose of $0.17 +/ - 0.10$ mg/kg.^(17,28) Only doses as high as 0.15mg/kg were found to be associated with significant adverse effects.⁽²⁹⁾

Potential Pitfalls (Study Limitations): Despite being a randomized study, there exists the possibility of bias due to unequal distribution of unknown covariates. The primary outcome of SAME is being measured using subjective pain scale of NAS and VDS for emesis. Although there are inherent limitations of such scales, we think they are widely used in practice and are well validated. We have considered a potency ratio of 1: 5 (M: HM) as it is commonly used and supported by the literature. However, we do accept that there is a much wider range described in some studies.

STUDY SIGNIFICANCE:

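### The secondary test of PACU opioid dose uses one 1:5 conversion, so it cannot separate a hydromorphone dose saving from a true potency ratio above 5

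*Combined protocol and SAP*

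**What the plan says.** - **Ratio.** PACU Stay states "We shall consider a potency ratio of 1:5 (M: HM), considered equivalent in literature" and builds the ratio into the blinded syringes: "1ml=1mg of morphine or 0.2 mg of hydromorphone".
- **Range.** The background describes hydromorphone as "5–10 times more potent". Potential Pitfalls defends 1:5 as commonly used, then adds: "we do accept that there is a much wider range described in some studies".
- **Outcome.** The first-listed secondary objective is "Total dose of analgesic used in PACU, in morphine equivalents". Table 1 measures it as "Dose of Analgesic used per patient in EMU" (EMU, morphine-equivalent units) and assigns a t test.
- **Test.** Statistical Analysis says: "Continuous outcomes will be analyzed using an unpaired 2-tailed student t test for significance", at p<0.05, with means, SDs and 95% CIs.
- **Sensitivity analysis.** The only one planned compares laparoscopic with open surgery. Nothing varies the conversion ratio, and no rule says how a dose difference will be interpreted.
- **Titration.** The PACU Protocol repeats boluses towards a pain score of 4/10 or less. Doses are also adjusted for side effects, withheld for sedation or respiratory depression, and supplemented by ketorolac rescue.

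**The concern.** One ml of study solution counts as one EMU in either arm, so the dose comparison for study drug is a comparison of volumes. If nurses titrate both arms towards the same pain score and hydromorphone is in truth more than five times as potent, patients on hydromorphone reach the target with fewer ml. The analysis would record that as a saving in morphine equivalents even if the two drugs were clinically identical.

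The ratio of 5 is the bottom of the protocol's own 5 to 10 range, so within that range the error runs one way, towards an apparent hydromorphone advantage. At stake is the meaning of the first-listed secondary result. Study Significance counts lower medication use among the perceived advantages, so a significant difference could easily be taken as support for that.

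**Working it through.** **The plan's own figure.** The only stated design calculation is for the primary outcome, 80% vs 90%, two-sided 0.05, 90% power. With pooled variance under the null:

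n = [1.960·√(2·0.85·0.15) + 1.2816·√(0.80·0.20 + 0.90·0.10)]² / 0.10² = (0.990 + 0.641)² / 0.01 = 265.9, so 266 per group.

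This agrees with the protocol. No power is stated for the dose outcome.

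**Inputs for the dose outcome.**
- Morphine requirement 0.17 ± 0.10 mg/kg (Risk Assessment and Protocol Adherence). Reading 0.10 as an SD is an assumption.
- 275 per arm (Sample Size Calculation).
- Conversion 1:5 (PACU Stay).
- True ratio r from 5 to 10 (background).

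**Model.** Assume equal clinical effect, so that hydromorphone dose expressed in EMU at 1:5 is 5/r of the morphine dose.

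- Apparent saving: d = 0.17·(1 − 5/r).
- Standard error, SD 0.10 in both arms: 0.10·√(2/275) = 0.00853.
- Standard error, hydromorphone SD scaled with its mean: √[(0.10² + (0.5/r)²)/275], which is 0.00785 at r = 6.
- Chance of p<0.05: P(|Z| > 1.96) with Z centred at d/SE.

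| True ratio | Apparent saving, mg/kg | Saving | Chance of p<0.05 (equal SD to scaled SD) |
|---|---|---|---|
| 5 | 0 | 0% | 0.05 |
| 5.5 | 0.015 | 9% | 0.44 to 0.47 |
| 6 | 0.028 | 17% | 0.91 to 0.95 |
| 7 | 0.049 | 29% | >0.99 |
| 10 | 0.085 | 50% | >0.99 |

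At r = 6, for example, d/SE is 0.0283/0.00853 = 3.32 or 0.0283/0.00785 = 3.61. At an assumed 70 kg, the saving is 2.0 mg at r = 6 and 6.0 mg at r = 10.

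**If some patients need no opioid.** Suppose 30% in each arm need none (an assumption). The morphine mean becomes 0.7·0.17 = 0.119, and its SD √[0.7·(0.10² + 0.17²) − 0.119²] = 0.114. The same formulas give about 0.20 to 0.21 at r = 5.5, 0.53 to 0.60 at r = 6, 0.94 to 0.98 at r = 7, and above 0.99 at r = 10.

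**Check with discrete boluses.** A simulation of 4,000 trials per setting used a lognormal requirement and steps of 0.04 then 0.02 mg/kg, without the first-dose cap or ml rounding. Rejection was 0.95 at r = 6 and 1.00 at 7.5 and 10. With 30% needing no opioid it was 0.57, 0.996 and 1.00. At r = 5 it stayed near 0.05.

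**The reverse case.** Equal volumes, 0.17 vs 0.17 mg/kg at 1:5, become 0.17 vs 0.34 when hydromorphone is converted at 1:10 (0.17·10/5). The comparison therefore depends on the ratio in either direction.

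**The case against.** The strongest reply has four parts.

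1. **The test is valid for what it tests.** It asks whether the two preparations, as made up, are needed in equal volume, and type I error for that question is not inflated. This stands. The difficulty lies in reading the answer as a difference in opioid requirement.

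2. **The range is disclosed and the data are recoverable.** Potential Pitfalls acknowledges it, and means and SDs will be reported, so a reader could multiply the hydromorphone figures by r/5. This stands too, and nothing is concealed. But disclosure attaches no analysis and no interpretation rule to the outcome, and the formal test is still made at one ratio.

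3. **Titration is not purely to pain.** Side effects, withholding, a first-dose cap, rounding and ketorolac rescue all affect the volume given, and the trial is powered on the expectation that success rates differ. A reader might infer that the EMU comparison mainly measures whether 1:5 is right. The documents do not support that; the comparison mixes the ratio with drug effects in unknown proportion.

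4. **The size is uncertain.** The 0.17 ± 0.10 mg/kg comes from other studies, whereas patients here also receive local infiltration and some may need no opioid. Table 1 measures dose per patient rather than per kg, so weight variation adds to the SD. These points lower the probabilities, most of all for ratios just above 5. They do not make a single-ratio difference interpretable.

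**Conclusion.** The concern holds for one secondary outcome. As written, the plan can report a statistically significant hydromorphone dose saving that comes from the conversion alone, and within the protocol's own range the error favours hydromorphone. The probability depends strongly on the true ratio: nominal at 5, somewhat under one half at 5.5, and 0.91 to 0.95 at 6, or about 0.55 at 6 if 30% need no opioid. It is at least 0.94 from 7 upwards in either case. These figures assume equal clinical effect, titration to a common endpoint and 0.10 as an SD.

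A reader might go further and infer that 1:5 is wrong, that a spurious saving is to be expected, or that the primary result is compromised. The documents show none of these. They support 1:5 as a common choice, do not establish the true ratio, and do not say that a lower EMU will be claimed as opioid-sparing. The primary analysis and the 266 per group are untouched.

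**What to change.** Before unblinding, add the following to the analysis plan:

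1. Keep EMU at 1:5 as the main presentation.
2. Report the actual mg of each drug, or ml of study solution, per arm with 95% CIs.
3. Pre-specify re-expression of the hydromorphone dose across the protocol's own range (for example 1:5, 1:7 and 1:10). State the ratio at which any difference disappears, which is 5 × (mean morphine ml / mean hydromorphone ml).
4. State that a difference at 1:5 alone will not be interpreted as opioid-sparing.

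I would not require the direction to hold at every ratio. Conversion at 1:10 doubles the hydromorphone figure, so a saving would survive only if it exceeded 50% at 1:5, while any hydromorphone excess would pass automatically. A true 30% saving with 1:5 correct would give hydromorphone-to-morphine ratios of 0.70, 0.98 (0.70·7/5) and 1.40 (0.70·10/5), and could not be claimed.

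Apply this to PACU study drug only. Table 1 times the dose outcome at hospital discharge, after possible oral opioids in the DSU for which no conversion is given. That timing should be reconciled with the objective.

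The cost is a short extra table, one sentence on interpretation and a weaker dose claim. No new data or patients are needed, and dosing does not change. The re-expression cannot undo any effect of the delivered doses on analgesia, emesis or sedation.
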